1 BACKGROUND

Ventricular tachycardia (VT) is a life threatening rhythm disturbance of the heart, which is associated with a significant risk of mortality as well as morbidity. VT is particularly prevalent in patients with ischaemic heart disease. Over the past three decades, catheter directed ablation has emerged as an increasingly useful adjunct to the implantable cardioverter-defibrillator (ICD) as treatment for this rhythm disorder, especially if medications fail, or are prohibited by side effects or patient choice. Traditional catheter ablation of VT uses several different invasive mapping methods to analyse the ventricular myocardium in detail and aims to modify those areas which are thought to be critical for sustaining the arrhythmic circuit. Commonly used techniques include activation mapping, entrainment mapping, pace-mapping and substrate mapping.

Activation mapping is a technique which, in cases of focal VT, records the earliest ventricular activation to find areas which are key in the generation of the arrhythmia, or in cases of re-entrant VT, to identify the diastolic pathway which allows the perpetuation of the arrhythmia¹.

Entrainment mapping is a technique whereby critical parts of the arrhythmia circuit can be identified by pacing at different locations, in an attempt to enter the excitable gap and capture the arrhythmia circuit. Once the critical isthmus utilised by the circuit is identified, ablation in this area can lead to termination of the arrhythmia.²

Both activation and entrainment mapping require a stable VT which is haemodynamically tolerated, which is often not the case. Therefore other methods of invasively mapping VT have been devised, most notably substrate mapping. Substrate mapping can be performed with the patient in sinus rhythm and is based on the fact that arrhythmogenic substrate in the ventricle produces different EGM signals from healthy tissue. Features of interest include fractionated signals, low voltage, split or double potentials, mid-diastolic potentials, late potentials and locally abnormal ventricular activity (LAVA)^{3,4}.

For some patients, particularly in those with non-ischaemic cardiomyopathy, scar is predominantly epicardial or mid-myocardial, meaning that endocardial mapping and ablation may be of limited efficacy⁵. In these cases, accessing the epicardium via a subxiphoid incision and performing additional ablation on the epicardial surface has been shown to be of benefit^{6,7}.

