Recently, data have emerged suggesting that computational modelling of a patient's heart based on 3D MRI reconstructions can enable prediction of optimal targets for VT ablation non-invasively. This has been confirmed in both retrospective and prospective studies.⁸ This involves high resolution MRI imaging with late-gadolinium enhancement (LGE) to assess the three-dimensional geometry of the scar, followed by reconstruction of the patient's heart *in silico*^{9,10}. Fibre orientation is established and overlaid onto this model¹¹. Standard electrophysiological properties are applied to the different categories of tissue as defined by the LGE signal intensity, namely, normal tissue, scar and grey zone. Using computational modelling, this "virtual heart" is then analysed for different potential ventricular tachycardia circuits that are theoretically sustainable based on the information supplied. A virtual electrophysiology study with programmed stimulation is conducted by virtually pacing the heart model from various different locations⁹. An algorithm is used to predict optimal ablation sites to terminate all possible VT circuits in this model heart. The algorithm initially generates "primary sites", which are the initial locations which have the potential to sustain ventricular tachycardia in the patient's heart. The model then undergoes virtual VT ablation of these primary sites and the prediction algorithm is re-run. This may generate a new VT-sustaining substrate and give predictions of "secondary sites" which can sustain VT in the post-ablation heart. The process is repeated until the heart is no longer VT-inducible.¹². In this way, not only should the patient's clinical VT be ablated, but all future potential ventricular tachycardias supportable by the substrate in its current form should also be avoided, reducing the need for repeat VT ablation.

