2 RATIONALE

Current invasive substrate mapping techniques are time and labour intensive. The ability to identify arrhythmogenic from non-arrhythmogenic areas within the same scar is limited, leading to prolonged procedure time and the potential overuse of ablative energy. Activation mapping during ventricular tachycardia, the gold standard for defining the critical isthmus sustaining the arrhythmia, is significantly limited by hemodynamic instability.

Image-guided VT ablation has been shown to improve substrate definition and may underpin improved outcomes in certain patient populations^{13,14}. Given the newly emerging field of personalised medicine and computation modelling this study will help to assess if an MRI-based, computer generated model accurately correlates to the invasive findings from an EP study with regards to targeting ablation in VT. If the model proves to be accurate, this will help to advance the process of *in silico* planning of VT ablation and potentially lead to improvements in outcomes of VT ablation, as well as reducing the need for repeated procedures. Results from the invasive studies can also be fed back into the computational model in an attempt to improve its accuracy. Furthermore, by assessing the electrophysiological properties of the computer generated predicted sites, we may learn which signals may indicate a critically important part of the VT circuit which traditional electroanatomical maps may miss.

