4.2 Outcome

- Assessment of the degree of validation of *in silico* computational modelling by invasive ventricular scar interrogation to see if the predicted sites match those sites which would have been determined as important from invasive mapping.
- Qualification of the electrophysiological characteristics of those sites which the computational model predicted in an attempt to see what it is about them that makes them likely to be key to maintaining the arrhythmia. With our mapping techniques, we can assess not only the amplitude and morphology

of the electrograms from these areas, but also the directionality of wavefronts to see if this is an important feature. With the additional benefit of the 3D computational model, we may be able to gain some insight into the 3D nature of channels which form part of the VT substrate.

- Assessment of the change in the invasive electrophysiological characteristics of distant sites following ablation of the primary predicted *in silico* sites. By ablating the predicted areas, it is possible that when we re-map distant points, they may be a change in their electrophysiological properties. There may be a change in variables such as the stim-QRS latency, the QRS morphology, the capture threshold and the nature of the exit site (e.g. multiple-exit site changing to single-exit site).
- Assessment of the frequency of ventricular arrhythmia, frequency of therapy delivered from an ICD (if applicable) and duration until first delivered therapy on serial heart rhythm monitors. Also assessment of patient's symptoms and adverse effects on clinical consultation.

5 STUDY DESIGN and METHODS of DATA COLLECTION AND DATA ANALYSIS

The study will be a single centre, prospective study based at St George's University Hospitals NHS Foundation Trust in London. Consecutive patients presenting to the hospital with an appropriate scar-dependent, sustained monomorphic ventricular tachycardia, requiring catheter ablation, will be screened for inclusion into the study. Full inclusion and exclusion criteria are listed below. Patients are likely to be predominantly outpatients, requiring elective VT ablation, however inpatients may also be included in the study.

If found eligible for the study, the patient will be approached by one of the study investigators and a Patient Information Sheet (PIS) will be offered. Written consent will be obtained if the patient is willing to proceed.

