If included in the study, de-identified, anonymized MRI images from patient's routine scan will be transferred to Johns Hopkins University, Baltimore Maryland, for computational analysis. The patient's MRI images will be reconstructed, analysed and a 3D geometric model of the patient's heart formed. From this, a computer-generated model of the patient's heart will be created. As described above, a virtual EP study, VT ablation and generation of both primary and secondary sites will be generated. The computation model as well as the locations of these primary and secondary sites will again be stored securely and transferred back to the primary research centre.

The patient will then undergo traditional endocardial, and in appropriate cases, epicardial, mapping and ablation of ventricular tachycardia, using the techniques previously described ^{1-3,7,15}. Patient preparation on the day of the procedure will be as for any other clinical VT ablation. Ablation technique will depend on whether or not there is a documented 12 lead ECG of the patient's clinical VT and also whether or not the VT is haemodynamically tolerated (stable) or not (unstable). This will be decided by the operator and will follow usual practice for VT ablation.

We will use a multipolar mapping catheter, in order to create a high-density map and gain as detailed information as possible about the substrate. Multipolar catheters are used as standard of care for VT mapping and ablation in our institution and most other high-volume specialised centres. The 3D computational model will be merged with the traditional 3D electroanatomical map generated during the VT ablation. Particular care will be taken when mapping the points of interest from the computational prediction to assess their particular electrophysiological properties. This will allow us to assess variables such as wavefront directionality, amplitude and morphology to see if they have a particular signal which marks them as important in sustaining the VT circuit and therefore conferring their importance in predicting potential sites for ablation. By overlaying the computer generated model onto the invasive map, we will be able to corroborate the predicted model's findings with traditional mapping techniques.

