7.3.3 Data collection tool

Each patient enrolled into the study will have a unique study trial ID number. This will allow the de-identification of all subsequent data associated with that patient. All subsequent data collection will be

transcribed next to this trial ID number in electronic format, through Microsoft Excel spreadsheets. There will be an electronic link document which will contain the patient identifiable information and the trial ID numbers, but no other data. This will be electronic and kept secure on password protected computers at St George's University, to which only the study investigators will have access. The link document will be kept until the results of the study have been analysed and written up. We anticipate that this will be complete within 3 years. The patient's consent will be kept in a locked area in the University.

Routine baseline demographics, risk factors and investigation results such as the patient's ECG and echocardiogram findings will be collected, de-identified and added to the Excel sheet. Primary data generated by the study will include the 3D computational model generated from the patient's cardiac MRI as well as data from the VT ablation including the baseline ECG, and electrograms during tachycardia and baseline rhythm. Individual data points from various endocardial and epicardial points will be collected by the mapping catheters which will contain information such as voltage, activation time, electrogram amplitude, directionality and morphology. Pacemaps and entrainment maps will be collected if these techniques are used. This data is generated by the cathlab software – Precision and Carto and will be de-identified, then transferred via USB stick to the password-protected excel spreadsheet with the appropriate trial ID number.

The data generated from the study will be stored for the duration of the study (3 years) and then archived onto secure, password-protected hard-drives. Paper documents will be archived with Iron Mountain for 5 years.

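### Aim 2 looks for a signal that marks predicted sites as important but states no contrast with non-predicted scar; secondarily, aim 3 states no rule for other lesions made between its two maps

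*Combined protocol and SAP*

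**What the plan says.** **Aim 2.** The second question in section 4 asks what the invasive properties of the predicted sites are. Three other places ask for more. Section 2 hopes that "we may learn which signals may indicate a critically important part of the VT circuit which traditional electroanatomical maps may miss". Section 4.2 characterises the predicted sites "in an attempt to see what it is about them that makes them likely to be key to maintaining the arrhythmia". Section 5 records wavefront direction, amplitude and morphology at these sites "to see if they have a particular signal which marks them as important in sustaining the VT circuit".

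Material for a comparison is foreseen. Section 4.1 includes characterising the ventricular scar by high-definition mapping. Section 5 plans a high-density map and says "The 3D computational model will be merged with the traditional 3D electroanatomical map generated during the VT ablation". Section 7.3.3 says "Individual data points from various endocardial and epicardial points will be collected by the mapping catheters". None of these places states a contrast of signals between predicted and non-predicted scar.

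**Aim 3.** The third question in section 4 asks whether ablating predicted sites changes distant sites, and section 4.2 limits that outcome to the primary predicted sites. Section 5 lets conventional mapping set the lesion sequence and calls for a re-map when an ablated area was also predicted. Section 8.1 confirms that areas judged important are ablated even where the model did not predict them. The visible text does not define the before map or say how other lesions in the interval are handled.

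**The concern.** A signal marks a site only if it is more common, or different, there than somewhere else. The background already states that "arrhythmogenic substrate in the ventricle produces different EGM signals from healthy tissue", so an abnormal electrogram at a predicted site is not distinctive by itself. The useful reference is other scar in the same heart, and the rationale names that difficulty for current mapping: "The ability to identify arrhythmogenic from non-arrhythmogenic areas within the same scar is limited".

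LGE category complicates the reading. In building the model, "Standard electrophysiological properties are applied to the different categories of tissue as defined by the LGE signal intensity", so predicted sites may differ from other scar in their mix of categories. A feature that only follows the category could then be reported as an independent marker of critical sites.

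For aim 3, a change caused by a lesion elsewhere could be credited to the predicted site.

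Both aims are exploratory, but they are two of the study's three stated questions.

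**Working it through.** The protocol gives no figure to reproduce here: section 7.2.1 sets at least 20 patients without an effect size, SD or precision target. The gaps are established by reading the sections together. Every input below is assumed unless a section is named.

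**Aim 2, no reference group.** If 14 of 20 patients show a feature at predicted sites, the estimate is 70%, with an exact 95% interval of 45.7% to 88.1%. Nothing in that result separates a frequency of 70% in other scar from one of 30%.

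**Aim 2, role of LGE category.** Suppose the signal depends on category alone. Let the grey-zone share be g1 at predicted points and g0 at other scar points, and the signal frequency be f1 in grey zone and f0 in dense scar. Then

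gap = [g1·f1 + (1−g1)·f0] − [g0·f1 + (1−g0)·f0] = (g1−g0)(f1−f0).

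- 0.3 × 0.2 = 0.06
- 0.5 × 0.2 = 0.10
- 0.3 × 0.4 = 0.12
- 0.5 × 0.4 = 0.20

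The unmatched gap is 6 to 20 points. Within a category it is 0. The two contrasts therefore answer different questions.

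**Aim 2, precision of a within-patient contrast.** In within-patient SD units, SE = √((τ² + 1/k + 1/c)/n), with k predicted sites and c comparison points per patient, and τ the between-patient SD of the difference. Take τ = 0.3, k = 3, n = 20 and c = 10: SE = √((0.09 + 0.333 + 0.1)/20) = 0.162. For a paired t test at two-sided 5% and 80% power the multiplier is 2.95 (0.660 × √20), so the detectable difference is 0.48 SD. With c = 20 it is 0.45, and with c = 5 it is 0.52. Over n of 15 to 20, k of 2 to 5, c of 5 to 20 and τ of 0 to 0.5, it runs from 0.33 to 0.76.

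**Aim 3, intervening lesions.** Take four ablated areas, two predicted (P) and two not (N), with a re-map after each P. If order is unrelated to the model, six sequences are equally likely, giving 12 re-maps. Count the re-maps with an N lesion since the before map:

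| Sequence | Before = latest map | Before = baseline map |
|---|---|---|
| PPNN | 0 | 0 |
| PNPN | 1 | 1 |
| PNNP | 1 | 1 |
| NPPN | 1 | 2 |
| NPNP | 2 | 2 |
| NNPP | 1 | 2 |
| Total of 12 | 6 (50%) | 8 (67%) |

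If the latest map covers the re-mapped points half the time, the share is (0.500 + 0.667)/2 = 58%. Next, give each predicted area three times, or one third, the weight of a non-predicted area at each step:

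| Order | Latest | Half | Baseline |
|---|---|---|---|
| Unrelated | 50% | 58% | 67% |
| Favours predicted threefold | 30% | 35% | 40% |
| Disfavours predicted threefold | 60% | 73% | 86% |
| Predicted always first | 0% | 0% | 0% |

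If all 20 patients gave two re-maps each, there would be 40 pairs. The clean ones, 40 × (1 − share), number 20, 17 and 13 with order unrelated, and 6 to 28 over the threefold range. Forty is itself an assumption, since a re-map happens only where a predicted area is ablated. These counts treat only non-predicted lesions as intervening. For any given re-map, counting secondary-site lesions as well can only add flags.

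**The case against.** The best defence of aim 2 is that its formal question is descriptive, its wider wording is tentative, and the comparison data are foreseen. All of that stands. A reader might infer that aim 2 cannot be delivered, or that nothing outside the predicted sites will be measured; sections 4, 4.1, 5 and 7.3.3 support neither reading. What remains is that the contrast is not stated. The comparison in section 4.2 of predicted with invasively important sites does not fill the gap, because it concerns whether locations agree and not how signals differ.

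The sentence on separating areas within one scar describes a limit of current mapping. It supports the choice of reference group but does not define aim 2.

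A reader might also treat every LGE-linked signal as a false finding. The fourth objective in section 4.1 contradicts that: it seeks the properties that probably led to a site being predicted, and LGE-linked ones qualify. A matched contrast alone could remove what that objective looks for, so the unmatched one is needed beside it.

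On aim 3, three objections stand. The flow chart is not shown and may give the map sequence. Section 4.2 names primary predicted sites, so a rule that ignores secondary-site lesions would not isolate the stated exposure. Pairs without intervening lesions are selected by the operator's order, so they are not an unbiased subset.

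**Conclusion.** The aim 2 point holds for the inference and not for the description. As written, the plan can report what electrograms at predicted sites look like; it cannot show that any feature marks those sites out. This rests on the text alone. The 6 to 20 points illustrate why two contrasts are needed and do not forecast a bias.

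The aim 3 point is secondary and partly unverifiable without the flow chart. Sections 5 and 8.1 together allow other lesions to intervene. A reader might take the 50% to 67% as the expected share of affected pairs. The documents do not support that: every input is assumed, and the results run from 0% to 86%.

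The change should be made before analysis, because a distance rule or before map chosen after seeing results would weaken either conclusion. Nothing here bears on what is ablated or in what order.

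**What to change.** **Aim 2.**
- Label mapped points as predicted by a distance from the predicted site on the merged map, fixed before analysis.
- Compare them with non-predicted scar points from the same patient's standard map, allowing for clustering within patient, for example with a patient random effect.
- Report two contrasts side by side: one unmatched, for the fourth objective in section 4.1, and one matched on or adjusted for LGE category and surface, to ask whether a signal adds to LGE category.
- Without these contrasts, report aim 2 as description only.

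**Aim 3.**
- Record lesion order and location.
- Use as the before map the most recent one that covers the re-mapped points.
- Flag each pair with any intervening lesion other than the primary predicted site, including lesions at secondary sites.
- Report all pairs and clean pairs side by side, noting that clean pairs over-represent areas the operator treated first.
- Word the conclusion as change after ablation, not as an effect specific to predicted sites.

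**Cost.** Extra analysis, mainly assigning an LGE category and a predicted or non-predicted label to each point. Error in merging the model with the map will blur both. Matching leaves fewer comparison points, the clean set is smaller, and precision stays exploratory at about 20 patients. The lesion log may already be kept, since the list in section 7.3.3 is not exhaustive; otherwise it is added to the data sheet. No extra patients are needed.

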Ablation technique will be as per standard of care and the order of ablation will be guided by standard invasive mapping. However if we ablate at an area which the MRI-model also predicted to be important, we will re-map the surrounding myocardium to see if there has been an effect of the electrophysiological properties of these distant sites following ablation of the predicted sites.. The computer model will not alter the extent of ablation and will not lead to ablation of any areas which wouldn't otherwise be ablated using traditional mapping.

The patients will be followed up as standard of care at 3, 6 and 12 months following their procedure with ICD interrogation, or in the case of absence of an ICD an extended ECG monitoring period. We will use this to assess frequency and duration of recorded arrhythmias time to recurrence of ventricular arrhythmia as well as frequency of therapy delivered by the device. We will also use data from their clinical consultation to evaluate their symptoms and response to the procedure including any adverse events.

STUDY FLOW CHART

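### Aim 3 asks about distant sites, but the methods re-map the surrounding myocardium with no rule separating the two, and paired pacing values are not guaranteed

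*Combined protocol and SAP*

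**What the plan says.** The third research question in section 4 asks whether ablating the predicted sites alters electrophysiological properties elsewhere in the ventricle. Section 4.2 states the matching outcome as "Assessment of the change in the invasive electrophysiological characteristics of distant sites following ablation of the primary predicted" in silico sites, and anticipates that "when we re-map distant points, they may be a change in their electrophysiological properties". As examples of what might change it gives "variables such as the stim-QRS latency, the QRS morphology, the capture threshold and the nature of the exit site", such as a site with several exits becoming one with a single exit.

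Section 5 supplies the method. Re-mapping is conditional: it happens "if we ablate at an area which the MRI-model also predicted to be important". The instruction is then "we will re-map the surrounding myocardium to see if there has been an effect of the electrophysiological properties of these distant sites". On ablation technique, the same section says "This will be decided by the operator and will follow usual practice for VT ablation".

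Section 7.3.3 lists what is recorded. The point data are illustrated by "voltage, activation time, electrogram amplitude, directionality and morphology". On pacing it says "Pacemaps and entrainment maps will be collected if these techniques are used".

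Section 8.1 limits the time added by co-registration, extra mapping of predicted targets and re-mapping to 10% of the usual duration. Section 8 puts this at roughly 30 minutes.

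**The concern.** The outcome and the method differ in two ways.

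The first is location. The aim concerns tissue remote from the ablated site, while the instruction covers tissue around it. Myocardium beside a lesion can be altered by the lesion itself, whether or not there is any remote effect. If the two are pooled, a local effect can be reported as the answer to a question about remote tissue.

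The second is measurement. A change needs a value before and a value after at the same point. Several of the variables that section 4.2 names exist only if the point is paced, and the collection plan makes pacing data optional.

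This is one of three stated research questions, and a pre-ablation value that was not recorded during the procedure cannot be recovered afterwards.

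**Working it through.** **1. Figures in the plan.** There is no figure for this outcome to reproduce. Section 7.2.1 gives at least 20 patients, with no error rate, power, effect size or precision target. The check is therefore mainly a comparison of sections.

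**2. Location.** Section 4 and section 4.2 both say distant. Section 5 says surrounding and, in the same sentence, calls that tissue distant. No section separates the two by distance, segment or lesion border, fixes the points to be compared, or names control points. An operator following section 5 literally would map around the lesion, and an analyst would have no rule for removing the points next to it. (Section 4.2 also refers to primary predicted sites, whereas the section 5 trigger is any predicted area.)

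**3. Direction of the error.** Let w be the share of re-mapped points that the lesion affects directly, L their mean change, and D the mean change at truly remote points. The pooled mean change is

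wL + (1 − w)D.

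If there is no remote effect, D = 0 and the pooled mean is wL. This is not zero whenever w > 0 and L is not zero, so change would be reported where the true answer to aim 3 is no change. The documents give neither w nor L, so the direction can be stated but not the size.

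**4. Variables.**

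| Variable | Needs pacing at the point? | In the section 7.3.3 examples? | Before and after values available? |
|---|---|---|---|
| Stim-QRS latency | Yes | No | Only if the same point is paced twice; not required |
| Capture threshold | Yes | No | As above |
| Exit type | Yes | No | As above |
| QRS morphology | Yes, if the paced QRS is meant; the text does not say | No; morphology there is of the electrogram | As above, on that reading |
| Voltage, activation time, electrogram amplitude, directionality, morphology | No | Yes | Whenever a re-map follows the initial multipolar map |

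Section 5 leaves ablation technique to the operator, and section 1 notes that substrate mapping can be done in sinus rhythm. A patient can therefore complete the protocol as written with no paired value for the first three variables.

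**5. How many patients would contribute.** Let a be the share of patients ablated at a predicted area and b the share of those with paired pacing values. The number contributing to the pacing variables is 20 × a × b. Neither share is given. Under assumed ranges of 0.5 to 1.0 for a and 0.25 to 1.0 for b, the result runs from 20 × 0.5 × 0.25 = 2.5 to 20 × 1 × 1 = 20. That range shows only that the protocol does not determine the number; it is not an estimate for this study.

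**The case against.** The pacing variables are introduced as examples; the outcome itself is the wider set of electrophysiological characteristics. A multipolar high-density map is planned without condition. The model is due before the procedure, so the predicted locations are known in advance, and re-mapping presupposes an earlier map. The list in section 7.3.3 is also illustrative, so leaving an item out does not prove that it will not be recorded. All of this stands. A reader might infer that outcome 3 often cannot be measured, but the documents do not support that. Section 1 says that stable VT is often lacking for activation and entrainment mapping only. It puts no such limit on pace-mapping, and no usage rate is given.

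It can also be said that the word surrounding appears once, in a sentence that itself says distant, and that nothing confines the re-map to the lesion edge. That is fair, and it rules out another tempting inference, that a positive answer is built into the design. It does not remove the problem. The one sentence that tells the operator where to map is the one that merges the two locations, and nothing elsewhere separates them.

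Finally, the model does not alter ablation, and the outcome is descriptive with no stated test. The consequence is therefore confined to how aim 3 is interpreted.

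**Conclusion.** The point holds in two parts. First, distant is undefined and is merged with surrounding in the only operating instruction. Local lesion effects can then be counted as distant change and bias aim 3 towards a positive answer. This rests on the text and on the premise that ablation can directly alter adjacent tissue. Second, paired values for stim-QRS latency, capture threshold and exit type are not guaranteed. Electrogram variables remain measurable wherever a re-map is done.

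The size of neither part can be calculated from the documents. The study remains feasible, but aim 3 cannot be interpreted clearly as written, and the plan should be changed before more maps are collected. I did not have the study flow chart in section 5, so the order of steps could not be checked against it.

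**What to change.** - **Outcome and analysis (sections 4.2 and 5).** Analyse outcome 3 as within-point change between the pre-ablation map and the re-map in voltage, activation time, and electrogram amplitude, morphology and directionality. Count as distant only points beyond a set distance from every lesion, with that distance fixed before any data are analysed. Report points inside it separately, as local lesion effect.
- **Wording (section 5).** Replace the reference to surrounding myocardium so that it matches this definition.
- **Data (section 7.3.3).** Add lesion locations to the exported data; the distance rule cannot be applied without them.
- **Pacing variables.** Report stim-QRS latency, capture threshold and exit type only for points with paired pacing values, and state how many patients and points contribute. Requiring paired pacing at fixed points would also close this gap, but it adds a measurement during the procedure and is not needed for the main correction.

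The cost is mostly wording and an offline distance calculation. Fewer points will count as distant, and the pacing variables will rest on a subset. If the re-map has to reach further out, the extra time must be reconciled with the 10% limit in section 8.1, which already covers co-registration and the extra mapping. The distance rule separates local from remote change. It does not show which of several lesions caused a remote change.
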